For participants who experience a delay in the study timeline (such as hospital admission, travel, short-term admission to a skilled nursing facility, etc.), the timeline will be adjusted accordingly. For example, if someone returns to the hospital during the intervention period and is in the hospital for 4 weeks, their T2 follow-up will be pushed back 4 weeks. If we can't schedule the T3 for three months past the normal time point for the T3, we will skip the T3 and schedule the T4.

Our primary outcome of the study is community participation. This has been severely limited by the current COVID-19 pandemic stay-at-home orders. We will adjust some of our follow up timepoints for data collection to reflect the SAH orders and allow people a chance to get back into the community before collecting community participation data. Our original timepoints are as follows: T2 (immediate post treatment), T3 (six months post stroke) and T4 (12 months post stroke). We will collect data at those timepoints but we are adding an additional collection time for each of those. Our T2COVID, T3COVID, T4COVID are all 60 days after the original T2/T3/T4 time point to allow for the SAH orders to lift and the participant to resume normal community participation. We will adjust these timepoints if the SAH orders continue longer than anticipated at this point.

Waiver of Consent: Retrospective Chart Review

At this time, we have consent to review medical charts during the enrollment and treatment process. However, we do not have permission to review the record after treatment was completed. Because we have ceased recruiting and all of our participants are finished with their participation in the study intervention and control groups, we no longer have contact with the majority of study participants. We would like to review medical charts (Wash U BJH medical records only) from participants who signed the Wash U COMPASS II consent form. We will collect limited data points, including date of death, hospitalizations, emergency room visits, and SNF/IPR admissions between their date of enrollment in this study and date of final study contact. For the waiver of consent, we will recruit participants already enrolled in this study.

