NIH Toolbox Instrumental Support Scale measures the availability of support for an individual to assist with completing daily tasks; 8-item scale, uses a 5-point likert scale response, scores are summed with higher score indicating more instrumental support.

10-Item Connor-Davidson Resilience Scale will measure resilience or ability to adjust to a stressful situation; consists of 10 items, all answered used a 5-point likert scale; total scores range from 0-40, with higher scores indicating greater resilience.

Healthcare Utilization and Mortality

Retrospective review of the medical records of all randomized participants to collect date of death, hospitalizations, emergency room visits, and skilled nursing facility (SNF)/Inpatient Rehabilitation (IPR) admissions between participants' date of enrollment until date of final study contact as a follow up metric to identify patient outcomes (see waiver of consent).

Statistical Analyses

Intention-to-Treat Analysis

We will perform our analyses using an intention-to-treat paradigm. We will perform exploratory data analysis looking for extreme or otherwise unusual values. Non-normal and heteroscedastic data will be transformed as necessary.

Baseline Analyses

We will use unpaired *t* tests and chi-square tests to compare T0 and baseline characteristics in the two groups for descriptive information (except when statistical assumptions are not met, in which case we may use Wilcoxon or Fisher exact tests).

Missing Data

We expect missing values in outcome measures because of dropout, death, missed assessment, or nonresponse. Our main analysis, a linear mixed-effects model, accommodates missingness due to treatment, prior outcome, or baseline covariates missing at random.⁸² Assuming that missing data occur at random, inferences will be valid even if we have differential dropout by intervention arm. If the missing data mechanism is not ignorable (ie, missing is not at random), then mixed-effects selection models or pattern-mixture models will be used.⁸³

Primary Analysis

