For the secondary analyses of the change in SIS score at 1 year and the change in I-HOPE at 1 year, we will use the same approach as for the primary analysis because these two outcomes are also continuous. We have overall type I error control for testing the 1-year change in these three analyses at the design stage. The significance level for testing is 0.016. In addition to comparison of 1-year change, we will extend the model by including scores immediately after intervention and at 6 months to see whether the difference in outcomes is achieved at those time points. Depending on the form of time variable in the model, we will use appropriate regression coefficients or a linear combination of the regression coefficients to determine the difference in change of these scores between arms at certain time points. Interpretation of these results should be cautious because we do not have the type I error controlled for these analyses. Because it is possible that severity of functional impairment after stroke may impact response to treatment, we will analyze impact of functional impairment on response to treatment. We will examine functional impairment by group interaction to examine possible differential intervention effects of functional impairment on community participation and performance of daily activities.

Safety

To determine whether the intervention poses no greater risk than AC, we will examine the differences in numbers of falls and rehospitalizations between groups. The statistical models for count data will be used for analyses of these two outcomes. Using the number of falls as an example, we will fit a Poisson regression model (with overdispersion adjustment if necessary), in which a dummy variable for the intervention arm is used. The regression parameter estimate for this dummy variable is the log of rate ratio of falls for COMPASS versus control arm, and exponentiation of the regression parameter estimate is rate ratio. Using the parameter estimate and its standard error, we can construct a two-sided 95% CI for the rate ratio. We expect the confidence interval for rate ratio will include 1, indicating no significant difference in the fall rate between the two groups.

Process Outcomes

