Evaluate acceptability and feasibility to aid in the interpretability of the trial. COMPASS will have high acceptability (80% retention), high fidelity by therapists (95% of elements and 90% of dose delivered), low safety risk (no increased rate of falls or health care use compared with the AC group), and high adherence (80% of modifications in use) at 12 months. We will conduct between-group comparisons of process endpoints collected at each time point (time to first fall, number of injurious falls, health care utilization rate, dosage delivered, and adherence rate) using unpaired *t* tests or chi-square tests. We will compare the characteristics of patients who complete the assigned intervention with those who do not for differences in stroke severity and comorbidities. Descriptive statistics will be used for costs per participant and adherence.

Sample Size Calculations

The study is designed to have 80% of power to reject three null hypotheses of equal mean changes in the primary and secondary endpoints (RNLI, SIS, and I-HOPE) using a two-sided, two-sample, unequal-variance *t* test with overall type I error <0.05 . Three alternative mean changes (standard deviation [SD] of change) in intervention and control populations are 15.3 (SD 22.6) versus 1.3 (SD 23.4) for RNLI, 15.7 (SD 16.1) versus 5.6 (SD 9.1) for the SIS ADL domain, and 62.1 (SD 26.1) versus 46.2 (SD 18.8) for I-HOPE. With a 1:1 allocation ratio, 130 patients (65 in each group) are needed for the RNLI outcome, 84 are needed for the SIS outcome, and 100 are needed for the I-HOPE outcome. We will enroll 180 patients to account for a 30% attrition rate. This magnitude of between-group difference is considered clinically meaningful based on prior relevant literature and is achievable based on our pilot study. Sample size calculation includes correlation between baseline and follow-up measures and is based on analysis of change scores, which is equivalent in efficiency to the proposed analytic model. Based on the number of stroke patient participants, we will enroll an equivalent number of caregivers.

Strengths and Limitations

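### The model for falls and rehospitalizations states no exposure term, so the rate ratio it reports would mix the event rate with any difference in follow-up between arms

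*Combined protocol and SAP*

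**What the plan says.** The Safety section of the statistical analyses sets the comparison in terms of counts: "we will examine the differences in numbers of falls and rehospitalizations between groups". Count models are to be used for both outcomes, and the model is written out with falls as the example: "we will fit a Poisson regression model (with overdispersion adjustment if necessary), in which a dummy variable for the intervention arm is used". The coefficient is then interpreted: "The regression parameter estimate for this dummy variable is the log of rate ratio of falls for COMPASS versus control arm". Of the interval the plan says "we can construct a two-sided 95% CI for the rate ratio", and of the result "We expect the confidence interval for rate ratio will include 1, indicating no significant difference in the fall rate between the two groups". No margin is given.

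These places determine how long each person is observed:

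- **Sample Size Calculations:** "We will enroll 180 patients to account for a 30% attrition rate".
- **Missing Data:** "We expect missing values in outcome measures because of dropout, death, missed assessment, or nonresponse". The method that follows is for the linear mixed model. It claims validity even when dropout differs by arm, but nothing comparable is said for the count models.
- **Follow-up Period for All Participants:** falls and health care use are collected by automated monthly telephone calls. The last planned visit is 12 months after stroke, and individual timelines may be shifted after delays.
- **Healthcare Utilization and Mortality:** the chart review runs from enrolment to each participant's last study contact.

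No section names an offset, an exposure time or a censoring rule for the counts.

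**The concern.** A Poisson model with an arm indicator and no offset compares mean counts per participant. Someone who leaves at month 2 without a fall then carries the same information as someone followed for 12 months without a fall. The coefficient is a log rate ratio only if mean follow-up is the same in both arms.

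The plan itself expects dropout and death, and participants are not blinded, so unequal follow-up is possible. The error favours whichever arm loses more people. If that were COMPASS, a real excess of falls or admissions would be shrunk towards the result the plan expects, an interval that includes 1. If it were control, a false signal against COMPASS could appear. Leaving the exposure term unstated also leaves the choice open until the data have been seen.

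**Working it through.** The Safety section gives no event rate, power or margin, so there is no figure of the plan's own to reproduce. The check is of what the stated model estimates.

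**Formula.** For an arm-only Poisson model,

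exp(coefficient) = mean count in COMPASS / mean count in control = true rate ratio × (mean follow-up in COMPASS / mean follow-up in control).

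**Inputs from the documents.** Overall attrition is 30%, allocation is 1:1 and nominal follow-up is 12 months.

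**Assumptions, because the documents give no figures.** These are the split of attrition by arm, the timing of loss, and a constant event rate. For a fraction d lost, mean follow-up as a share of 12 months is:

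- loss spread uniformly over the year: 1 − d/2
- all losses at 3 months: 1 − 0.75d

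**Factor applied to the true rate ratio.** Each split averages 30%.

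| Loss, COMPASS / control | Uniform loss | All lost at 3 months |
|---|---|---|
| 30% / 30% | 0.850/0.850 = 1.00 | 0.775/0.775 = 1.00 |
| 35% / 25% | 0.825/0.875 = 0.94 | 0.7375/0.8125 = 0.91 |
| 40% / 20% | 0.800/0.900 = 0.89 | 0.700/0.850 = 0.82 |
| 20% / 40% | 0.900/0.800 = 1.13 | 0.850/0.700 = 1.21 |

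With a true ratio of 1.20 and 40%/20% loss, the arm-only model gives 1.20 × 0.889 = 1.07 (uniform) or 1.20 × 0.824 = 0.99 (all at 3 months). With 35%/25% it gives 1.20 × 0.943 = 1.13 or 1.20 × 0.908 = 1.09.

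**Simulation check.** This used 90 per arm, 4000 runs, uniform loss, an assumed rate of 1.5 events per person-year and frailty variance 1.

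| Loss, true ratio | Arm-only estimate | With person-time |
|---|---|---|
| 30%/30%, 1.00 | 1.00 | 1.00 |
| 40%/20%, 1.00 | 0.89 | 1.01 |
| 40%/20%, 1.20 | 1.07 | 1.20 |

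The simulation agrees with the formula, and dividing by person-time recovers the true ratio when loss is unrelated to the event rate.

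**The case against.** **The plan may intend an offset.** It speaks of a rate ratio and a fall rate, gives the model only as an example, and never says that the arm indicator is the sole term. This stands. A reader might infer that person-time has been excluded, but the documents support only that no exposure term is specified.

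**The bias is conditional.** No split of attrition by arm is given, and equal follow-up leaves the ratio unbiased. The 30% figure sizes the efficacy sample and is not stated to be loss from the monthly calls. A 40% loss in COMPASS is twice the 20% implied by the 80% retention target under Process Outcomes. If COMPASS met that target and overall loss were 30%, control loss would be 40% and the error would run against COMPASS. This stands too: the size is illustrative and the direction is not known in advance.

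**Imprecision may matter more than the offset.** With 90 per arm, full follow-up, 1.5 falls per person-year and frailty variance 1, the variance of the log ratio is 1/135 + 1/162 + 2/90 = 0.0358, so the standard error is 0.189. An estimate of 1.20 then has a 95% interval of about 0.83 to 1.74. Without overdispersion it is about 0.95 to 1.51. Under these assumptions the interval includes 1 with or without an offset, so it would be wrong to infer that the missing offset alone would hide a 20% excess. The point estimate and the position of the interval are still affected.

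**Other comparisons exist.** Process Outcomes also compares time to first fall, injurious falls and a utilization rate, so this is not the only safety comparison. Those use t tests or chi-square tests, which do not handle unequal follow-up in fall times or counts.

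**The timeline rule is weak support.** One might read "their T2 follow-up will be pushed back 4 weeks" as showing that a readmission lengthens the counting period. The example moves an assessment visit, and the text does not say that the window for falls or admissions moves with it.

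**Conclusion.** The point holds as a gap in specification with a predictable consequence. As written, the model yields a ratio of mean counts per participant under the name of a rate ratio, and the two differ by the ratio of mean follow-up. At the planned 30% overall attrition that factor is 1.00 if loss is equal and equally timed in the two arms, about 0.91 to 0.94 at 35%/25%, and about 0.82 to 0.89 at 40%/20%. Reversing the last split gives about 1.13 to 1.21. These values rest on assumed splits, assumed timing of loss and constant event rates.

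The documents do not show that the safety ratio will be biased, or that COMPASS will look safer than it is. They show that the stated model gives no protection if follow-up differs. The change is worth making because safety is a named aim and the remedy is cheap. The primary endpoint is not affected.

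**What to change.** In the Safety section, add the log of each participant's observed person-time as an offset in the models for both outcomes, and define the time as follows:

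- **Falls:** months covered by completed monthly calls, from randomisation to the earliest of death, withdrawal or 12 months after stroke. A month without a completed call contributes neither events nor time.
- **Rehospitalizations:** time from enrolment to the earliest of death, final study contact or 12 months after stroke, counting only events inside that window. Time after final contact must not be counted, because the chart review collects no admissions there. Counting all days to 12 months would bring the same bias back.

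Report person-time and deaths by arm beside each rate ratio.

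The cost is a few sentences and some derivation. The chart-review dataset is already to hold last-contact, death and hospitalization dates, and call responses are transferred to REDCap, so months with a completed call should be derivable, although the documents do not say that call dates are kept. The interval may become slightly wider or less favourable. The offset also assumes that dropout and unanswered calls are unrelated to falling or admission. State that limit or add a simple sensitivity analysis.

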Primary Outcome(s)	
Specific Aim 1 (Primary): We will compare the efficacy of a novel enhanced rehabilitation transition program (COMPASS) and an equivalent dose of attentional control for significant improvements in community participation and ADL performance and a reduction in environmental barriers in the home and community after stroke.
 
Specific Aim 2 (Secondary): We will evaluate alternative primary outcome measures of participation, function, patient-reported quality of life, and caregiver burden that permit comparison to other stroke clinical trials and confirm the safety of COMPASS.
 
Specific Aim 3 (Secondary): We will evaluate process outcomes such as reach, cost, fidelity, and adherence to aid interpretability of the trial and future implementation.
 
Primary Endpoint: Reintegration to Normal Living Index (RNLI). The RNLI measures the extent to which a person is able to resume normal life activities after illness or injury.¹ The 11-item questionnaire quantifies participation (basic self-care, functional mobility, avocational and productive pursuits, travel in the community), with a higher score indicating higher attainment of normal levels of living. The RNLI is a valid and reliable² measure that is well-aligned with the primary aim of this trial. The scale demonstrated excellent internal consistency,³ construct and content validity,^{2,3} and interrater reliability.² The RNLI is brief and can be administered in person or by telephone.
 
Secondary endpoints: Stroke Impact Scale (SIS) ADL Domain. The SIS is a stroke-specific assessment of health-related quality of life (participation, ADLs, mobility, hand function, strength, memory, communication, emotion). It has demonstrated high content validity⁴ and construct validity.⁵ The SIS domains have excellent internal consistency (Cronbach $\alpha = 0.83\text{--}0.90$)⁶ and test-retest reliability (Interclass correlation range 0.7–0.92),⁶ and discriminate across four Rankin levels of stroke severity ($P \leq 0.01$).⁶ The SIS ADL domain demonstrated a moderate (0.44) effect size in our pilot.
 
The In-Home Occupational Performance Evaluation (I-HOPE) to measure ADL performance and magnitude of environmental barriers in the home. The I-HOPE is a performance-based, multistep, client-centered assessment that evaluates the performance of older adults doing 44 activities in the home. Four subscales measure limitations in daily activities, self-reported performance and satisfaction with performance of problematic activities, and the magnitude of environmental barriers that influence performance. I-HOPE assessment is commonly used in occupational therapy (OT) to provide home modification interventions. The instrument yields four subscales with high internal reliability ($\alpha = 0.77\text{--}0.78$) and interrater reliability ($\alpha = 0.94\text{--}1.0$)⁷ and is sensitive to change in environmental support.
 
Exploratory endpoints: Our goal is to optimize the design of a phase III multicenter trial; therefore, we will examine additional endpoint measures to evaluate their utility in the trial setting. These measures

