Stroke is a leading cause of disability in the US. Most stroke survivors have difficulty performing daily activities and participating in the community. Efficacy of interventions that address the chronic needs of stroke survivors has been identified as a high priority for stroke research. A gap in care exists at the point of transition from inpatient rehabilitation (IR) to home, when survivors encounter new environmental barriers due to the cognitive and sensorimotor sequelae of stroke. Resolving these barriers and improving independence in the community have potential to significantly improve stroke survivors' long-term morbidity. The proposed study investigates the efficacy and safety of a novel, enhanced rehabilitation transition program to reduce environmental barriers and improve daily activity performance and community participation. Community Participation Transition after Stroke (COMPASS) uses two complementary evidence-based interventions: home modifications and strategy training delivered in the home. Home modifications provide environmental support to compensate for impairments. Strategy training enables patients to identify and prioritize ADL problems, identify barriers to performance, and develop strategies to resolve barriers. The complementary effects of these therapies at a novel point of care offer a robust intervention for a current service gap. The primary aim of this phase IIb, single-blind, parallel-group, randomized controlled trial is to investigate the efficacy of COMPASS during the transition from IR to home. Participants will be randomized to receive either COMPASS or attentional control. We hypothesize that COMPASS participants will demonstrate significant improvements in community participation and ADL performance and a significant reduction in environmental barriers versus control. In preparation for a phase III multicenter trial, we will explore additional candidate study endpoints and establish intervention safety by examining the rates of falls and hospital readmissions. Finally, we will conduct a process evaluation examining outcomes such as reach, cost, fidelity, and adherence to aid interpretability of the trial and implementation. The aims fill critical gaps in stroke rehabilitation evidence by investigating the efficacy, safety, and implementation of an intervention targeting the transition from an acute to a chronic condition. The results of this trial will provide important information about the long-term participation and environmental barriers of stroke survivors. The project has the potential to resolve the significant unmet need of disability after stroke.

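### The aim of showing COMPASS carries no greater risk has no rule beyond a confidence interval expected to include 1, and time to first fall is given tests that ignore censoring

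*Combined protocol and SAP*

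**What the plan says.** The safety aim is worded as a positive finding in four places.

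- Specific Aim 2 (Primary Outcome(s) entry of the World Health Organization Data Set) is to "permit comparison to other stroke clinical trials and confirm the safety of COMPASS".
- The Abstract says the trial will "establish intervention safety by examining the rates of falls and hospital readmissions".
- The Safety section opens with "To determine whether the intervention poses no greater risk than AC".
- Process Outcomes states in advance that COMPASS will have "low safety risk (no increased rate of falls or health care use compared with the AC group").

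For the analysis, the Safety section fits a Poisson model with an arm indicator to falls, as the example for falls and rehospitalizations. It adjusts for overdispersion if needed and forms a two-sided 95% confidence interval for the rate ratio. The only statement on how to read it is "We expect the confidence interval for rate ratio will include 1, indicating no significant difference in the fall rate between the two groups".

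Process Outcomes lists "time to first fall, number of injurious falls, health care utilization rate, dosage delivered, and adherence rate" and assigns the between-arm comparisons to unpaired t tests or chi-square tests. Falls are collected monthly by automated phone call (Follow-up Period for All Participants). The Missing Data section says "We expect missing values in outcome measures because of dropout, death, missed assessment, or nonresponse". It adds that "inferences will be valid even if we have differential dropout by intervention arm", but this is said of the linear mixed model used for the main analysis.

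**The concern.** There are two separate problems.

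**Reading the safety comparison.** The aim is to show that risk is not raised. The expected result is that no difference is detected. These are different conclusions: the fewer the events, the wider the interval and the more easily it includes 1. Without a margin or a rule for the upper limit, imprecision alone can meet the expectation. The power statement covers only RNLI, SIS and I-HOPE, so nothing in the design assures a precise safety estimate. The conclusion matters because this phase IIb trial is meant to prepare for a phase III trial.

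**Time to first fall.** Anyone who leaves, dies or reaches the end of follow-up without a fall has a censored time. Neither a t test nor a chi-square test accounts for that. If the arms lose participants at different rates, these tests can show a difference that is not there or hide one that is. No section mentions log-rank, Cox, Kaplan-Meier or censoring.

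Monitoring of individual participants and reporting of serious adverse events are not affected.

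**Working it through.** The plan gives no fall rate, dispersion, margin or power for safety, so there is no safety figure to reproduce. What follows rests on stated assumptions.

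**1. How often the interval includes 1**

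Inputs:
- 180 enrolled at 1:1, so 90 per arm (Sample Size Calculations).
- 30% attrition (same section), assumed uniform over one year: mean follow-up 0.7 × 1 + 0.3 × 0.5 = 0.85 years.
- Assumed: control rate 1 fall per person-year (range 0.5–2) and dispersion φ = 2 (range 1–4).

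Expected control falls: E0 = 90 × 0.85 × 1 = 76.5. COMPASS falls: E1 = E0 × RR.

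SE(log RR) = √(φ/E0 + φ/E1)

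P(interval includes 1) = Φ(1.96 − log RR/SE) − Φ(−1.96 − log RR/SE)

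- RR 1.5: SE = √(2/76.5 + 2/114.75) = 0.209; log 1.5/SE = 0.405/0.209 = 1.94; probability 0.507.
- RR 1.25: SE = √(2/76.5 + 2/95.6) = 0.217; 0.223/0.217 = 1.03; probability 0.823.
- Largest estimate x whose interval still includes 1 solves log x = 1.96 × SE(x). This gives x = 1.505, with upper limit x² = 2.27.
- Chance that the upper limit falls below an illustrative 1.5 when the true ratio is 1: SE = √(4/76.5) = 0.229; Φ(0.405/0.229 − 1.96) = 0.426.

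| Quantity | Central | 2 falls/year, φ = 1 | 0.5 falls/year, φ = 4 |
|---|---|---|---|
| Interval includes 1, true RR 1.25 | 82% | 46% | 92% |
| Interval includes 1, true RR 1.5 | 51% | 3% | 84% |
| Largest estimate with interval including 1 (upper limit) | 1.51 (2.27) | 1.24 (1.53) | 2.15 (4.64) |
| Upper limit below 1.5, true RR 1 | 43% | 94% | 14% |

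Simulating overdispersed counts with a person-time offset and estimated dispersion (4,000 trials) gave 49.9%, 81.4% and 43.8%, against 50.7%, 82.3% and 42.6% by formula. A different variance model, var(log RR) = (1/μ0 + k)/n + (1/μ1 + k)/n, with 65–90 per arm, one year, 0.5–2 falls per year and k = 0–2, gave 39–90% at a ratio of 1.25 and 1–77% at 1.5.

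**2. Time to first fall**

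Assumed: exponential times, one-year horizon, 50% of controls falling within the year, 90 per arm, dropouts censored uniformly. The plan does not say how people without a fall enter a t test; they are entered at their censoring time. The tests are Welch t on observed time, chi-square on ever fell (no continuity correction) and log-rank. There were 10,000 trials per scenario, with Monte Carlo error at most 0.7 points.

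| Scenario | t | Chi-square | Log-rank |
|---|---|---|---|
| No effect, 30% dropout in both arms | about 5% | about 5% | about 5% |
| Hazard ratio 1.6, 30% in both arms | 43% | 53% | 62% |
| No effect, 25% v 35% | 9–10% | 5–6% | 5% |
| No effect, 20% v 40%, either arm losing more | 22% | 9% | 5% |
| Hazard ratio 1.6, COMPASS loses 40%, control 20% | 82% | 27% | 61% |
| Hazard ratio 1.6, COMPASS loses 20%, control 40% | 11% | 77% | 61% |

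With 35–65% of controls falling and dropout 20% v 40% (5,000 trials), false positives are 16–32% (t), 7–12% (chi-square) and 5% (log-rank). In the last two rows the true effect is the same, so the swing in the t and chi-square columns comes from which arm loses more. Rejection rates above log-rank there are bias, not power.

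**The case against.** The quoted sentence is a forecast, not a decision rule, and it says only that no significant difference is expected. The plan estimates a rate ratio, allows for overdispersion and forms an interval, so a reader can see the upper limit. That is true, and it confines the first problem to what may be claimed. It does not supply the missing link to a conclusion of no greater risk.

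The sizes rest on assumed fall rates and dispersion, and the ranges are wide. That also stands. The central figures illustrate the problem and are not forecasts for this trial. With frequent falls and no overdispersion, an increase of one half would seldom be missed. Rehospitalization was not quantified.

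Time to first fall is one of several process endpoints, and the main fall comparison is the count model. The largest errors need unequal dropout and people without a fall entered at their censoring time. With equal dropout the false-positive rate holds. These points limit the weight, but two replies remain. First, the stated goal of 80% COMPASS retention, with 30% attrition overall, would be compatible with 20% v 40% (the average of 20 and 40 is 30), although the plan states no control-arm figure. Second, restricting the t test to fallers does not help. In a separate simulation (1 first fall per person-year, hazard ratio 1.75, no dropout) its power was 22%, against 89% for log-rank.

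Enrolment is closed, so a margin set now is not a design-stage choice. That is a fair weakness, and the option of making no claim avoids it.

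**Conclusion.** Both parts hold and should be fixed. The stated expectation cannot support a conclusion of no greater risk. Under the central assumptions it would be met in about half of trials with a true 50% increase in falls (3–84%) and in 82% with a 25% increase (46–92%). Time to first fall needs a method that handles censoring. The gain is certain but modest if dropout is equal (power 62% against 43% and 53% at hazard ratio 1.6). It is larger if dropout is clearly unequal, when false positives reach about 22% (t) and 9% (chi-square) at 20% v 40%. Neither part touches the primary efficacy analysis.

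**What to change.** 1. State that an interval including 1 will not be read as no greater risk or no increased rate. Interpret the upper 95% limit of the rate ratio. Claim no material increase only if it lies below a margin that the sponsor fixes, with reasons, before unblinding; otherwise report the estimate and interval as inconclusive. If no margin is set, report the estimate and interval without the claim, and bring the wording of Aim 2, the Abstract and Process Outcomes into line.
2. Analyse time to first fall by log-rank or Cox, censored at the last answered monthly call. Say how deaths, earlier missed calls and times known only to the month are handled.
3. Minor: write out the log person-time offset in the Poisson model. The plan's talk of rates already implies it.

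The cost is analysis-plan wording; no new data are needed. The price is that the safety conclusion may well be inconclusive, and that a late margin carries less weight than one set at design. Log-rank and Cox still assume that dropout is unrelated to fall risk.
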